9.3.2. Demographic and Baseline Characteristics

The following patient's demographic and baseline characteristics will be collected:

- Only at study inclusion:
 - Age (MONYYYY);
 - Gender (Male/Female);
 - Height;
 - Socio-professional status;
 - Date of OSA diagnosis (MONYYY);
 - Relevant medical history including (but not limited to) the following past cardiovascular risk factors:
 - Arterial hypertension, defined according to international guidelines, or the current use of antihypertensive drugs (international non-proprietary name);
 - Atrial fibrillation;
 - Diabetes mellitus (Type 1 or Type 2);
 - Hypercholesterolemia (HDL and LL cholesterol) (6.42 mmol/l in peripheral blood or current use of treatment);
 - Stroke, or transient ischemic attack;

- Ischemic heart disease with or without myocardial infarction;
- Carotid stenosis (more than 50% Doppler).
- At study inclusion and at each follow-up visits:
 - o Weight;
 - Waist circumference;
 - Smoking status:
 - Never smoker;
 - Former smoker. If yes, number of pack-year and the year when they stopped smoking:
 - Current smoker. If yes, number of pack-year.
 - Current daily alcohol consumption (in glass: 1 glass = 10 g alcohol);
 - Physical activity (sport duration per week [hours]);
 - O Duration of sleep (hours) as reported by the patients;
 - Perceived sleepiness at driving (assessment of 4 questions) (will not be done at the 6month follow-up visit).

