9.3.8. Prior and concomitant medications or therapies

OSA primary therapy

The use of CPAP of alternative therapy (e.g., MAD) will be collected both at study inclusion and at each follow-up visits. The following data will be collected:

- Start date (MONYYYY);
- o Mean number of hours of use per night during the last three months;
- Discontinuation (Yes/No). If yes: date and primary reason of discontinuation.
- Prior and concomitant medications

Prior (last three months before inclusion) and concomitant medications will be recorded as text fields. The data on prior medication will be collected only at study inclusion. The data on concomitant medications will be collected both at study inclusion and at each follow-up visits. For concomitant medications, the dosage regimen, the route of administration, and the dates of use will also be collected.

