9.7.5. Primary Analyses

The main objective of the study is to demonstrate that OZAWADE® supplementation does not increase CV events compared with control (non-inferiority). The following analysis will be conducted:

The annual CV morbidity incidence will be estimated by the occurrence of CVE per patient per year equivalent to the proportion of patients with at least one CVE.

The CV risk is known to be higher for OSA patient with existing CV history, using or not CPAP, and well-known risk factors: diabetes, cholesterol, weight, hypertension, demographics (age, gender), lifestyle (fitness, alcohol use, smoking habits).

A generalized linear mixed model featuring Poisson regression will be based on a post stratification model based on the following fixed covariates or random effects:

- nCVE_b, prior CV history measured by the number of CV events experienced before baseline, expected as the essential predicting covariates;
- Risk factors (RF): diabetes, cholesterol, weight, hypertension, alcohol use, and smoking habits reported at baseline;
- Demographics: gender, age, country, study center
- Matched classes propensity clusters: the treatment will be non-randomized but determined by the investigator, involving an expected imbalance between groups on baseline conditions. The decision of prescribing a given medicine will be assumed on a set of baseline covariates defined in the statistical plan. As too many covariates are expected, finding sufficient exact matches is unfeasible, and the goal of subclassification is to form matched subclasses (clusters), such that in each the distribution of covariates for the treated and control groups are as similar as possible. The propensity score will be used as the scalar distance with a two-stage algorithm starting with the nearest neighbour matching and optimized by a full matching procedure [39, 40, 41].

The final model is:

CVE ~ $nCVE_b + \Sigma_i RF_i + gender + age + trt + \{country\} + Offset (log-exp) + \{center | country\} + \{cluster\}$

The notation Σ_i RF_i covers the above mentioned considered risk factors. The obvious effect of the exposure duration is measured by the offset of its logarithm. The last fixed factor is the treatment (trt) binary effect (0=control, 1=pitolisant). Country, site effect nested within country, and cluster (matched group) effects will be used as random factors (between {}).

Sensitivity Analysis

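### The primary model has no fixed term for physical activity or primary therapy, although Section 9.7.5 names fitness as a CV risk factor, mentions CPAP use, and both are collected at inclusion

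*Protocol*

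**What the plan says.** All the modelling text is in Protocol Section 9.7.5.

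- **Risk statement.** "The CV risk is known to be higher for OSA patient with existing CV history, using or not CPAP, and well-known risk factors". The sentence runs on: "using or not CPAP, and well-known risk factors: diabetes, cholesterol, weight, hypertension, demographics (age, gender), lifestyle (fitness, alcohol use, smoking habits".
- **Covariate list.** "Risk factors (RF): diabetes, cholesterol, weight, hypertension, alcohol use, and smoking habits reported at baseline". The other model terms are the number of prior CV events, gender, age, treatment, the log-exposure offset, country, centre within country, and matched cluster.
- **The list is closed.** The summation term in the final model "covers the above mentioned considered risk factors".
- **Propensity score.** "The decision of prescribing a given medicine will be assumed on a set of baseline covariates defined in the statistical plan". Its only route into the model is the cluster term: "Country, site effect nested within country, and cluster (matched group) effects will be used as random factors".

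Both missing variables are on the data collection plan. Section 9.3.8 records CPAP or alternative therapy at inclusion and follow-up, including "Mean number of hours of use per night during the last three months". Section 9.3.2 records weekly hours of sport at inclusion and at each follow-up visit. Section 9.3 adds that no assessment is obligatory and that only available measures are entered. Apart from the description of CPAP adherence (9.7.6.2), primary therapy enters the analysis only in Section 9.7.9, as a subgroup presentation that may be made.

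**The concern.** The primary claim is non-inferiority on cardiovascular events in a non-randomised comparison, so it depends on the adjustment. The section sets out which factors drive CV risk and then fixes a model that leaves out one of them (fitness), and on one reading a second (CPAP use), without giving a reason.

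The inclusion criteria admit patients with and without primary therapy, so primary therapy varies in this population. The physician chooses the treatment, and Section 9.7.5 itself expects baseline imbalance between the groups. If primary therapy or activity is related both to that choice and to CV events, the rate ratio is shifted. A shift below 1 could hide harm and support a false non-inferiority conclusion. A shift above 1 could create a false signal.

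**Working it through.** **Step 1: risk statement against model terms (Section 9.7.5).**

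| Factor in the risk statement | Fixed term in final model | Collected at inclusion |
|---|---|---|
| CV history | yes (number of prior events) | yes (9.3.2) |
| Diabetes, cholesterol, weight, hypertension | yes | yes |
| Age, gender | yes | yes |
| Alcohol, smoking | yes | yes |
| Fitness | **no** | yes, weekly sport hours (9.3.2) |
| CPAP use (wording ambiguous) | **no** | yes, use and hours per night (9.3.8) |

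Fitness is the only factor listed after the colon that has no term. The cluster term may or may not reflect fitness or CPAP, because its covariates are left to the SAP.

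**Step 2: what one omitted factor could do.** The protocol gives no prevalence or risk ratio for either variable, so every input here is assumed. For one unadjusted binary factor with prevalence p1 (exposed) and p0 (unexposed) and risk ratio g, the rate ratio is multiplied by

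[1 + p1(g − 1)] / [1 + p0(g − 1)]

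- p1 = p0 = 0.5: 1.00 for any g.
- 0.6 vs 0.4: g = 1.2 gives 1.12/1.08 = 1.04; g = 1.5 gives 1.30/1.20 = 1.08; g = 2 gives 1.60/1.40 = 1.14.
- 0.3 vs 0.5, g = 1.5: 1.15/1.25 = 0.92. Reversed: 1.25/1.15 = 1.09.
- 0.2 vs 0.6, g = 2: 1.2/1.6 = 0.75. Reversed: 1.6/1.2 = 1.33.

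The formula ignores the cluster term and any overlap with covariates already in the model, so it shows the bias with no adjustment at all for the factor.

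**Step 3: would the propensity score alone repair it?** A random intercept is shrunk towards zero and is assumed independent of treatment. Full matching gives clusters with different treated-to-control ratios. A cluster's risk level can then be associated with its share of treated patients, and a shrunken intercept only partly absorbs that. This was simulated with 195 patients per group (the sizes in Section 9.9), a true rate ratio of 1.00, primary-therapy non-use **included** in the score, approximate full matching, a Poisson mixed model, 200 runs per cell and assumed rates of 0.1 to 0.6 events per patient:

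| Non-use, exposed vs unexposed; risk ratio | No propensity term | Random cluster term |
|---|---|---|
| 30% vs 50%; 1.5 | 0.93 to 0.95 | 0.93 to 0.95 |
| 20% vs 60%; 2 | 0.75 to 0.77 | 0.79 to 0.81 |
| 60% vs 20%; 2 | 1.30 to 1.42 | 1.23 to 1.39 |

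With non-use as a fixed covariate, the ratio was 0.98 to 1.07 across all cells.

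A second simulation of the same kind gave 0.92, 0.79 and 1.24 with the cluster term, against 0.92, 0.75 and 1.30 without it, and 0.97 to 1.01 with the fixed covariate. On the log scale, ln 0.79 / ln 0.75 = 0.236/0.288 = 0.82 and ln 1.24 / ln 1.30 = 0.215/0.262 = 0.82. About four fifths of the bias remained in those two cells.

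**The case against.** **Confounding is not established.** A reader might infer that the plan leaves avoidable confounding in place. The documents do not show this. The model also has propensity clusters, introduced because imbalance is expected, and their covariates are properly left to an SAP that is not at hand. The protocol neither includes nor excludes these two variables there. That objection stands against any claim of proven confounding. It does not remove the point, because the protocol itself fixes how the score acts, and Step 3 suggests that this route recovers little.

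**CPAP is not clearly named as a risk driver.** The phrase can mean that CPAP use affects risk, or that risk is higher whether or not the patient uses CPAP. CPAP also stands before the colon that opens the list of factors. Fitness has no such ambiguity.

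**The label does not imply imbalance.** It is tempting to argue that CPAP use must differ because the indication covers both inadequately treated and intolerant patients. But every patient, prescribed or not, must be eligible under the SmPC, and enrolment is consecutive. Both groups come from the same mixed population. Imbalance is plausible because physicians choose, but nothing documents its size or direction.

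**The range 0.75 to 1.33 is not the bias of this study.** It needs a 40-point imbalance together with a doubled risk, and ignores overlap with weight, hypertension and prior events. The simulation results are also conditional: they depend on the assumed inputs and on the clusters that the matching produces.

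**The remedy has a cost.** Collection is availability-only, so extra fixed terms could drop patients with missing values.

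**Conclusion.** The point holds as an inconsistency within Section 9.7.5 with a plausible consequence. Fitness is named as a CV risk factor and CPAP use is mentioned, yet the closed covariate list and final model have no fixed term for physical activity or primary therapy, although both are planned for collection at inclusion. This risks residual confounding of the non-inferiority rate ratio if either variable differs between the groups.

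The size and direction are unknown. With balance the factor is 1.00, and moderate assumed imbalances give shifts of roughly 4% to 14%. Relying on the propensity score alone would, under the assumptions simulated, leave most of such bias. The text of the sample-size section and its appendix is not available, so the bias cannot be set against the non-inferiority margin. The change should be made because it is specific and cheap, not because harm to the estimate has been shown.

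**What to change.** 1. Add to the fixed part of the primary model in Section 9.7.5: baseline primary-therapy status (none / CPAP / MAD), with hours of use per night where available, and baseline physical activity.
2. Name the same variables as required covariates of the propensity score.
3. Reword the CPAP phrase so that it says either that CPAP use is treated as a risk factor or that risk is raised regardless of CPAP use.
4. State a missing-value rule for these covariates, either a missing category or imputation, so that no patient drops out of the primary analysis.

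The cost is a few more parameters, the missing-data rule, and an edit to the protocol formula and the SAP. No new data collection is needed. Section 9.7 has the SAP finalised before the first interim database lock, so the change should be settled by then.

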7.1. Background

Obstructive Sleep Apnoea (OSA) is a highly prevalent chronic disease affecting nearly 1 billion people aged 30–69 years worldwide [1]. OSA is characterized by repetitive collapses of the upper airway during sleep, resulting in intermittent hypoxia, leading to secondary sympathetic activation, oxidative stress and systemic inflammation [2]. The diagnosis of OSA is based on the apnoea-hypopnoea index (AHI) – that is the number of apnoeas and hypopnoeas per hour of sleep, as determined by standard overnight polysomnography –, and the presence of other symptoms such as daytime sleepiness or fatigue [3, 4]. According to the American Academy of Sleep Medicine, OSA is classified as mild with AHI of 5–15, moderate with AHI of 16–30, and severe with AHI > 30 [3]. The mechanisms of OSA are multifactorial, including obesity, craniofacial changes, alteration in upper airway muscle function, and pharyngeal neuropathy [2]. OSA is recognized as associated with poor health outcomes, including cardiovascular diseases (mainly hypertension), diabetes, cognitive deficits and early mortality [2, 5-8].

Excessive daytime sleepiness (EDS) is a prominent symptom of OSA and is associated with a higher incidence of concentration difficulties, impaired vigilance, depressive symptoms, and increased risk of accidents [9, 10]. This impairment in daily functioning and deterioration in quality of life results in considerable economic and societal burdens. EDS has been reported to affect 12 to 58 % of people with OSA [11-13]. The variations in EDS prevalence could be explained by different factors such as the nature of EDS and the variety of factors impacting its presentation, the overlap with other comorbidities and the existence of various tools for EDS assessment. The Epworth Sleepiness Scale (ESS) is the most commonly used self-administered assessment for EDS [14]. The ESS evaluates the propensity to fall asleep in common real-world situations. A cut-off of > 10 points in the ESS is accepted to indicate EDS [15-17].

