- 8. Although the data will be limited for patients not using primary therapy, the data can be systematically collected from CPAP softwares in those under CPAP during the follow-up visits.
- 9. CPAP or alternative primary treatment adherence will be reported as the mean number of hours of use per night.

PASS protocol 3.0 – 23 NOV 2023

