9.3. Variables

The data collected will be those data that the investigating centers are used to assess during routine visits, exception made of some Clinician- or Patient- Reported Outcomes (ClinROs, PROs) questionnaires (see below) planned to properly answer to the study objectives. The following assessments have no obligation to be performed and only the available measures and assessments will be collected in the CRF.

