9.3.6. Disease activity

OSA and EDS will be evaluated according to routine clinical practice by the tool and ClinROs/PROs questionnaires described below:

• Apnoea-hypopneoa index (AHI)

The AHI is a diagnostic tool for determining the presence and severity of OSA. AHI is measured with CPAP device or by polysomnography. It is calculated by dividing the total number of apnoeic and hypoapnoeic events by the total number of hours of sleep by night. The data can be systematically collected from CPAP software in those under CPAP during each follow-up visits. AHI data will be collected both at study inclusion and at each follow-up visit.

• Epworth Sleepiness Scale (ESS)

The ESS is a short validated self-administered questionnaire (PRO) to measure a subject's usual level of daytime sleepiness or average sleep propensity [14, 34]. It is composed of 8 questions, each describing a different daily life situation. Each question is rated on a 4-point scale (0-3) and total ESS score is obtained by summing the scores of the eight items (0-24). The higher the ESS score, the higher that person's average sleep propensity in daily life or their daytime sleepiness. ESS data will be collected both at study inclusion and at each follow-up visit.

Maintenance of wakefulness test (MWT) or Multiple Sleep Latency Test (MSLT)

The MWT is a validated polysomnographic test for the evaluation of daytime sleepiness/wakefulness [35]. It evaluates a subject's ability to remain awake while resisting the pressure to fall asleep during soporific circumstances.

MSLT evaluates the tendency to fall asleep under controlled conditions [36]. The test consists of four to five naps given two hours apart during the day, following a standardized procedure. Both tests allow the measure of the mean sleep latency as the measure of sleepiness.

MWT and MSLT data will be collected both at study inclusion and at each follow-up visit (except for the 6-month follow-up visit).

• Fatigue Severity scale (FSS)

The FSS is a validated self-report scale of nine items which measures the severity of fatigue and its effect on a patient's activities and lifestyle. Answers are scored on a seven point scale (1-7). The total FSS score is obtained by summing the score of the nine items (9-63). The higher the score, the more severe the fatigue and the more it affects the person's activities. FSS data will be collected both at study inclusion and at each follow-up visit (except for the 6-month follow-up visit).

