9.7.4. Disposition, Demographic, and Baseline Characteristics Analyses

Disposition of patients, demographics, and all baseline characteristics (as described in Section 9.3.2) will be summarized overall on the study population and by treatment group (OZAWADE® vs non-OZAWADE®).

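### OSA severity (AHI) is collected at inclusion but named in no analysis, so adjustment for it in the non-inferiority estimate is not assured

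*Protocol*

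**What the plan says.** The protocol treats AHI as its measure of severity. Section 9.3.6 states: "The AHI is a diagnostic tool for determining the presence and severity of OSA". Section 7.1 grades OSA by AHI as mild (5–15), moderate (16–30) or severe (above 30), and links the disease to cardiovascular outcomes: "OSA is recognized as associated with poor health outcomes, including cardiovascular diseases (mainly hypertension".

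On collection, Section 9.3.6 says: "AHI data will be collected both at study inclusion and at each follow-up visit". Table 2 specifies the value at diagnosis of OSA, and separately the follow-up values with or without CPAP.

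On analysis, Section 9.7.4 limits its by-group description to "all baseline characteristics (as described in Section 9.3.2) will be summarized overall on the study population". Section 9.3.2 contains the date of OSA diagnosis but not AHI. Section 9.7.5 gives the risk factors as "Risk factors (RF): diabetes, cholesterol, weight, hypertension, alcohol use, and smoking habits reported at baseline" and then states the final model: prior CV events, those risk factors, gender, age and treatment as fixed terms, a log-exposure offset, and country, centre within country and propensity cluster as random effects. The covariates behind the propensity score are deferred to the statistical plan.

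Two statements bear on data availability. Section 9.3 says: "The following assessments have no obligation to be performed and only the available measures and assessments will be collected in the CRF". A footnote to Table 2, on AHI at follow-up, adds: "Although the data will be limited for patients not using primary therapy, the data can be systematically collected from CPAP softwares".

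**The concern.** Treatment is chosen by the physician, and Section 9.7.5 itself expects the groups to differ at baseline. The severity of the disease that defines the cohort is an obvious candidate confounder. It may influence whether a wake-promoting drug is added, and it may influence the rate of cardiovascular events. If it does both and is left out, the treatment rate ratio is biased. A bias below 1 is the harmful direction here, because it makes a non-inferiority conclusion on cardiovascular safety easier to reach.

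The baseline description matters for the same reason. If AHI is not shown by group, a reader of the report cannot see whether the exposed and unexposed patients had comparable disease.

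**Working it through.** **Step 1: look for AHI in each analysis section.**

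| Section | What it names | AHI? |
|---|---|---|
| 9.7.1 | age and gender of enrolled vs not enrolled | no |
| 9.7.4 | disposition, demographics, 9.3.2 items | no (AHI sits in 9.3.6) |
| 9.7.5 fixed terms | prior CV events, six risk factors, gender, age, treatment | no |
| 9.7.5 propensity cluster | covariates left to the SAP | not stated |
| 9.7.6 Cox model | time-varying covariates, not listed | not stated |
| 9.7.6.1 | ESS, MWT/MSLT, FSS | no |
| 9.7.6.2 | adherence to OZAWADE and CPAP | no |
| 9.7.7 | adverse events, ECG, blood pressure, heart rate, depression score | no |
| 9.7.8 | abdominal perimeter, weight, biology, traffic accidents | no |
| 9.7.9 | primary therapy use | no |

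No section names AHI. Two places leave room for it without naming it: the propensity cluster and the Cox covariates.

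**Step 2: size of the effect if severity were wholly uncorrected.** The protocol gives no figure to reproduce. Neither the share of severe OSA per group nor the effect of severity on the CVE rate is stated, so both are assumed. Let R be the CVE rate ratio of severe to non-severe OSA, and p1 and p0 the shares with severe OSA among exposed and unexposed patients. The treatment rate ratio is then multiplied by

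[1 + (R − 1)·p1] / [1 + (R − 1)·p0]

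| p1 vs p0 | R = 1.2 | R = 1.5 | R = 2.0 |
|---|---|---|---|
| 55% vs 45% | 1.11/1.09 = 1.018 | 1.275/1.225 = 1.041 | 1.55/1.45 = 1.069 |
| 60% vs 40% | 1.12/1.08 = 1.037 | 1.30/1.20 = 1.083 | 1.60/1.40 = 1.143 |
| 65% vs 40% | 1.13/1.08 = 1.046 | 1.325/1.20 = 1.104 | 1.65/1.40 = 1.179 |

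If the imbalance runs the other way, the factors are the reciprocals, from 1/1.018 = 0.982 to 1/1.179 = 0.848.

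**Step 3: what already absorbs part of it.** Hypertension, weight and prior CV history are fixed terms. Section 7.1 says the cardiovascular association is mainly with hypertension and names obesity among the mechanisms of OSA, so part of any severity effect would run through terms already in the model. The cluster term may take up more, depending on the SAP. The table is therefore the uncorrected case, not a forecast.

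**The case against.** A reader might infer that AHI enters no analysis at all and that imbalance in severity stays uncorrected. The protocol does not support that. Section 9.7.5 provides a specific tool for baseline imbalance, the propensity subclasses, and leaves their covariates to an SAP that is not shown. AHI may be among them. The Cox model in 9.7.6 likewise does not list its time-varying covariates. This part of the objection stands.

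The confounding premise is also not established by the document. The indication turns on sleepiness that is not satisfactorily treated, or on intolerance of primary therapy, not on AHI class. Section 7.1 links OSA as a disease to cardiovascular outcomes without giving a gradient by AHI, and every enrolled patient has OSA. The list of known CV risk drivers in 9.7.5 does not include AHI. This stands too: both links are plausible assumptions.

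A reader might also conclude that a shift of this size would decide the non-inferiority test. That cannot be judged, because no margin is visible in the public text.

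Finally, it can be said that a baseline table row and a covariate list are SAP detail. This holds for the propensity covariates, and 9.7.4 does not forbid extra rows. It does not hold for the primary model, whose risk factor list and equation are written out here. An SAP that follows them has no fixed AHI term. Nor does the cluster make a fixed term redundant. The protocol enters CV history, risk factors, age and gender as fixed effects alongside it, and a random intercept is shrunk towards the mean, so it may adjust only in part.

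**Conclusion.** The point holds as a gap in commitment. The protocol collects its own severity measure at inclusion, omits it from the stated primary model and from the stated scope of the by-group baseline summary, and names it in no other analysis. Adjustment for OSA severity therefore depends on a propensity covariate list that is not shown.

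Under the assumed inputs, a wholly uncorrected imbalance would raise the rate ratio by about 2% to 18%, or lower it by about 2% to 15% if reversed. The real shift would be smaller to the extent that hypertension, weight, CV history and the clusters absorb it. It would be nil if severity affected only one of prescribing and CVE rate, or neither. The change is worth making because it is cheap and the value is already scheduled, not because bias has been demonstrated.

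**What to change.** - **Section 9.7.5:** add AHI at diagnosis as a fixed covariate, either in the three classes of Section 7.1 or as log AHI, and name it as a required propensity covariate.
- **Section 9.7.4:** add AHI at diagnosis to the by-group summary, with the number missing in each group.
- **Which value:** specify the diagnostic value for every patient. AHI read from a CPAP device reflects treated disease and is not comparable between CPAP users and non-users.
- **Missing values:** keep patients without a recorded diagnostic AHI in the analysis, by a missing category or by multiple imputation, since assessments are optional under Section 9.3. Section 7.1 bases the diagnosis on AHI, so most patients should have a value.

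The cost is one degree of freedom for log AHI or two for three classes (one more if a missing category is used), one table row, and some missing-data handling. No new data collection is needed.
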